Title of the study: Daily Weight Feedback for Wheelchair Users to Promote Weight Loss

NCT number: 03264248

Date: June 5th, 2018

[\[reviewer notes→\]](#)**Provide a short title for this study** (200 characters or less):**Daily weight feedback for wheelchair users to promote weight loss****T1.0****Select the type of application:**

New Research Study

T2.0**Is the proposed research study limited to the inclusion of deceased individuals?**

* No

T2.1**Are any research activities being conducted at the VA Pittsburgh Healthcare System or with VA funds?**

* No

[\[reviewer notes→\]](#)**T3.0****What is the anticipated risk to the research participants?**

Minimal Risk

T3.1**Why do you feel that all aspects of this research study, including screening and follow-up, involve no more than minimal risk to the research subjects?**

This study is a standard behavioral weight loss study focusing on diet, physical activity, and behavioral strategies to effectively make lifestyle changes. It will also include using a new scale (E-scale) which has minimal risk as it will continuously record the weight of the bed which will allow for capturing the weight of the person when they are in bed.

T4.0**Does the proposed study qualify for 'exempt' IRB review or for a determination of either 'not research' or 'no human subject' involvement?**

* No

T5.0**Does the proposed research study qualify for 'expedited' IRB review status?**

* Yes

[\[reviewer notes→\]](#)**CS1.0 What is the reason for this submission?**

New Research Protocol Submission

CS1.1**Has this research study been approved previously by the University of Pittsburgh IRB?**

* No

CS1.1.1**Has this research study (or a substantially similar research study) been previously disapproved by the University of Pittsburgh IRB or, to your knowledge, by any other IRB?**

* No

[\[reviewer notes→\]](#)**CS2.0****Title of Research Study:****Daily weight feedback for wheelchair users to promote weight loss****CS2.0.1****Requested approval letter wording:****CS2.1****Research Protocol Abstract:**

The goals of the proposed study are to test the usability, feasibility and preliminary efficacy of the E-Scale with wheelchair users. Up to fifteen overweight or obese wheelchair users will be enrolled in a 13 week study that includes standard behavioral treatment (SBT) for weight loss that focuses on diet, physical activity, and behavioral strategies (e.g., goal setting, self-monitoring) to support lifestyle changes specifically for people with mobility impairments. The subjects will also be provided the E-scale to track their weight daily. The primary outcomes will be usefulness (subjective feedback from a survey about the program/E-scale), feasibility (accuracy and repeatable measurements from the E-scale) and efficacy (improvements in weight and other measures of health) of the weight loss program coupled with the E-scale at the end of 13 weeks. The results could inform the refinement of this technology to increase its applicability for wheelchair users to independently monitor their weight in their own homes while attempting to lose weight.

CS2.2**Select the category that best describes your research:**

Hybrid - includes aspects of BOTH types of research (check this option if your research is mainly social/behavioral but also involves specimen collection or blood draws to look at biological measures)

[\[reviewer notes→\]](#)**CS3.0 Name of the Principal Investigator:**

Note: Adjunct faculty of the University, including lecturers and instructors, are not permitted to serve as a PI or Faculty Mentor but may serve as co-investigators. Refer to [Chapter 4](#) on the HRPO website for more information.

CS3.1 Affiliation of Principal Investigator:

UPitt faculty member

If you chose any of the **Pitt options**, please indicate the specific campus:

[Main Campus - Pittsburgh](#)

If you chose the UPitt faculty member option, provide the PI's **University Faculty Title**:

Associate Professor

CS3.2 Address of Principal Investigator:

[name]
[name]

CS3.3 Recorded Primary Affiliation of the Principal Investigator:

U of Pgh | School of Health and Rehabilitation Sciences | Rehabilitation Science and Technology

CS3.4 Identify the School, Department, Division or Center which is responsible for oversight of this research study:

[U of Pgh | School of Health and Rehabilitation Sciences](#)

CS3.5 Telephone Number of Principal Investigator:

[contact]

Name Modified Date

Is this research study supported in whole or in part by industry? This includes the provision of products (drugs or devices).

* No

Is this a multi-centered study?

* No

[\[reviewer notes→\]](#)

CS12.0 Does your research protocol involve the evaluation or use of procedures that emit ionizing radiation?

* No

CS13.0 Does this research study involve the deliberate transfer of recombinant or synthetic nucleic acid molecules into human subjects?

* No

Upload Appendix M of NIH Guidelines:

Name Modified Date

CS14.0 Are you using UPMC facilities and/or UPMC patients during the conduct of your research study?

* No

If Yes, upload completed Research Fiscal Review Form:

Name Modified Date

[\[reviewer notes→\]](#)

CS15.0

Indicate the sites where research activities will be performed and/or private information will be obtained.

Choose all sites that apply and/or use **Other** to include sites not listed:

Sites:

University of Pittsburgh

University of Pittsburgh

Campus:

Main Campus - Pittsburgh

List university owned off-campus research sites if applicable:

Bakery Square

If you selected **School, International or Other**, list the sites:

***For research being conducted at non Pitt or UPMC sites, upload a site permission letter granting the researcher permission to conduct their research at each external site:**

Name Modified Date

CS15.1 Have you, [name], verified that all members of the

research team have the appropriate expertise, credentials, and if applicable, hospital privileges to perform those research procedures that are their responsibility as outlined in the IRB protocol?

* Yes

CS15.2

Describe the availability of resources and the adequacy of the facilities to conduct this study:

* Our facilities at the Human Engineering Research Laboratories has all of the capabilities needed to conduct this study. We have the equipment needed to conduct the baseline and final measurements (scale, body-fat monitor, and tape measure). We have a locked file room and protected servers for consent and other confidential information. There is a private room for conducting screening and consent procedures. The study has been fully funded by a grant from the Paralyzed Veterans of America foundation.

[\[reviewer notes→\]](#)

CS16.0 Special Research Subject Populations:

Categories

None

[\[reviewer notes→\]](#)

CS17.0 Does your research involve the experimental use of any type of human stem cell?

* No

[\[reviewer notes→\]](#)

NIH Definition of a Clinical Trial

A research study¹ in which one or more human subjects² are prospectively assigned³ to one or more interventions⁴ (which may include placebo or other control) to evaluate the effects of those interventions on health related biomedical or behavioral outcomes.⁵

¹ See Common Rule definition of research at [45 CFR 46.102\(d\)](#) .

² See Common Rule definition of human subject at [45 CFR 46.102\(f\)](#) .

³ The term “prospectively assigned” refers to a pre-defined process (e.g., randomization) specified in an approved protocol that stipulates the assignment of research subjects (individually or in clusters) to one or more arms (e.g., intervention, placebo, or other control) of a clinical trial.

⁴ An intervention is defined as a manipulation of the subject or subject’s environment for the purpose of modifying one or more health-related biomedical or behavioral processes and/or endpoints. Examples include: drugs/small molecules/compounds; biologics; devices; procedures (e.g., surgical techniques); delivery systems (e.g.,

telemedicine, face-to-face interviews); strategies to change health-related behavior (e.g., diet, cognitive therapy, exercise, development of new habits); treatment strategies; prevention strategies; and, diagnostic strategies.

⁵ Health-related biomedical or behavioral outcome is defined as the pre-specified goal(s) or condition(s) that reflect the effect of one or more interventions on human subjects' biomedical or behavioral status or quality of life. Examples include: positive or negative changes to physiological or biological parameters (e.g., improvement of lung capacity, gene expression); positive or negative changes to psychological or neurodevelopmental parameters (e.g., mood management intervention for smokers; reading comprehension and /or information retention); positive or negative changes to disease processes; positive or negative changes to health-related behaviors; and, positive or negative changes to quality of life.

CS18.0 * Based on the above information, does this study meet the NIH definition of a clinical trial?

Yes No

If Yes, click Save and then [Click Here For Study Team's CITI Training Records](#) . Please ensure all personnel's training is up to date

[\[reviewer notes-\]](#)**1.1 Objective: What is the overall purpose of this research study? (Limit response to 1-2 sentences.)**

To determine the usefulness, feasibility and efficacy of the E-scale system coupled with a standardized behavioral treatment weight-loss intervention for overweight or obese wheelchair users.

1.2 Specific Aims: List the goals of the proposed study (e.g., describe the relevant hypotheses or the specific problems or issues that will be addressed by the study).

Aim 1. To investigate the usefulness and feasibility of the E-scale system and efficacy of the E-scale coupled with a weight-loss intervention to assist overweight or obese wheelchair users with losing weight.

Hypothesis 1a: The E-scale will be useful based on self-reported feedback from wheelchair users by more than 50% stating that the E-scale is easy to use, their preferred weight monitoring system, them feeling that they would use the E-scale if it was available for them to purchase.

Hypothesis 2b: The E-scale will be feasible by providing accurate (+/- 2 lbs. from a calibrated scale measurement) and repeatable (<3lbs difference from day-to-day) weight measurements and by the wheelchair users continuing to use the scale more than 70% of the days of the study.

Hypothesis 2c: The E-scale coupled with the weight loss intervention will demonstrate efficacy by wheelchair users having significant improvements in weight, abdominal girth, body fat percentage and score on the Self-Rated Abilities for Health Practices Scale (SRAHP).

1.3 Background: Briefly describe previous findings or observations that provide the background leading to this proposal.

Wheelchair users have about twice the prevalence of obesity than the general population. There is also very little or no technology to which they have access to measure their weight frequently in their homes. Research however, has shown that monitoring your body weight frequently (i.e. daily) yields significantly better weight loss and weight maintenance results. This research has never included wheelchair users because they have not had access to technology to be able to measure their weight daily. The E-scale was developed as a weight monitoring technology for wheelchair users and has been tested for precision and accuracy in the laboratory.

1.4 Significance: Why is it important that this research be conducted? What gaps in existing information or knowledge is this research intended to fill?

This research will tell whether wheelchair users find the E-scale to be useful and feasible as a way to monitor their weight in their homes. It will also show whether wheelchair users, like the general population, have better weight loss outcomes if they monitor their weight daily. This could lead to refinement of the E-scale and a push for more available technology for wheelchair users to monitor their weight at home which could in turn lead to a decrease in the prevalence of obesity among wheelchair users.

[\[reviewer notes ↴\]](#)

2.1 Does this research study involve the use or evaluation of a drug, biological, or nutritional (e.g., herbal or dietary) supplement?

* No

[\[reviewer notes ↴\]](#)

2.2 Will this research use or evaluate the safety and/or effectiveness of one or more devices?

* Yes

2.2.1 Does this research study involve an evaluation of the safety and/or effectiveness of one or more devices not currently approved by the FDA for general marketing?

* Yes

If YES, describe your **plan to prevent unauthorized use of the investigational device**: The E-scale is a non-invasive device which measures the weight of each of the four legs of a bed. As such there would be no benefit or harm from unauthorized use.

2.2.1.1 List each of the unapproved devices being evaluated in this research study.

Specify for each listed device the corresponding Investigational Device Exemption (IDE) number or provide a justification for why you feel that this device and its use, as proposed in this research study constitute a non-significant risk (i.e., to include potential failure of the device) to the research subjects:

Unapproved IDE device	#	Non-significant risk justification
View E-scale		The E-scale is a set of weight sensors for each leg of a bed. This device does not have potential for serious risk to the health, safety, or welfare of a subject since (1) The device is not an implant; (2) The device is not used in supporting or sustaining human life; or (3) The device is not of substantial importance in diagnosing, curing, mitigating, or treating disease, or otherwise preventing impairment of human health. It has also been used in the home without any adverse events in IRB # PRO14080007

[\[reviewer notes ↴\]](#)

2.2.2 Does this research study involve the use or evaluation of the safety and/or effectiveness of one or more devices approved by the FDA for general marketing?

* No

[\[reviewer notes ↴\]](#)

2.3 Summarize the general classification (e.g., descriptive, experimental) and methodological design (e.g., observational, cross-sectional, longitudinal, randomized, open-label single-blind, double-blind, placebo-controlled, active treatment controlled, parallel arm, cross-over arm) of the proposed research study, as applicable.

This study will be experimental. It will be a 13 week longitudinal efficacy study.

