Potential subjects will be screened over the phone or in person with a list of questions that may exclude them from the study. If it is determined that they are likely to be eligible, they will be asked to contact their doctor for a letter approving their participation in a weight loss program and scheduled to come to the lab where they will be consented into the study. They will also be asked to record their diet for 3 days to determine if they are willing to comply with this key component of the study. When they come into the lab, informed consent will be performed first. After the consent process is complete, subjects will be given the Center for Epidemiologic Studies Depression Scale (CES-D) and the Eating Disorder Diagnosis Scale (EDDS) to determine if they would be considered to have a current eating disorder or are currently depressed. Next the subject's weight and height will be measured in the lab by having the subjects drive onto a calibrated roll-on scale to get the weight of their chair with them in it. Then they will transfer out of their wheelchair (with assistance of the research team or trained member of our lab if requested) onto a mat table where they will be asked to lay flat on their back so that their height can be measured with a tape measure. While they are on the mat table, a member of the research team will take their chair back to the roll-on scale to weigh the chair. The subject's weight will be determined by subtracting the weight of the chair from the weight of the subject in the chair. The subject's Body Mass Index (BMI) will then be calculated. They will then transfer (or be assisted) back to their chair.

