After the subjects' have been determined to be eligible, they will have their abdominal girth measured with a tape measure and their body-fat percentage will be measured with a hand-held BIA inductance measuring tool. They will also be given a demographics questionnaire and the Self-Rated Abilities for Health Practices questionnaire to answer. The LoseIt! (diet and activity journal) and E-scale apps will be installed on their phones/android devices or they will be provided with an android device with the apps already installed to use during the study. De-identified login and passwords will be provided to the subjects to use during all of the study procedures so no identifiable data will ever be collected by these apps. Some training on use of the E-scale and LoseIt! apps will be provided to the subjects as well as the first lesson of the 13-week curriculum. Over the next few days, the study team will go to all of the subject's homes to install the E-scale under their beds.

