During the next 12 weeks, subjects will be asked to weigh themselves every day with the E-scale app and record their diet, exercise and weight every day with the LoseIt! app. The data that is reported in the LoseIt! app by the subjects will be monitored by the study team using the ascendapp for LoseIt!, which allows a "coach" to monitor all of the data submitted by a client. The weight loss curriculum involves weekly lessons for the participants to learn and practice things like counting calories and fat, reorganizing their kitchens, doing more cardio work around the house, etc. This curriculum was adapted from the Diabetes Prevention Program Group Lifestyle Balance (DPP GLB) curriculum at Pitt specifically for people with mobility impairments. The study team will send periodic emails with comments to the participants encouraging their progress and adherence to the protocol and lesson materials for that week. Every week at a pre-defined time, a group chat room will be conducted with all of the subject's and the research team invited to attend to go over the lesson for that week and to have a group discussion for the participants to share successes and difficulties with the group. The chat room will be hosted using Adobe Connect with the audio and video capabilities disabled. The link to the chat room for each week will be emailed to the subjects along with the lesson materials. The curriculum disbursement, progress emails, and chat rooms will be led by a dietitian/nutritionist with experience in leading group weight loss programs.

During the last week of the study (week 13). The subjects will be asked to come back to the lab in-person where their weight will again be measured using the roll-on scale. Their

abdominal girth and body-fat percentage will also be measured again. The SRAHP will be administered to the subjects again and they will also be given the final questionnaire, System Usability Scale (SUS), which will evaluate how they felt about the E-scale and some aspects of entire study. Any android devices that were loaned to the subjects during the study will be collected and the apps on their personal devices will be deleted if they wish. Over the next few days, the study team will visit all of the subject's homes to remove the E-scales or the participants can bring them with them to the lab.

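### Hypothesis 2b's under-3-lb day-to-day limit mixes body-weight change with device error, so a failure cannot by itself be blamed on the E-scale; its ±2 lb limit has a usable reference weight but no stated pairing

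*Combined protocol and SAP*

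**What the plan says.** Hypothesis 2b in section 1.2 sets two measurement limits: "providing accurate (+/- 2 lbs. from a calibrated scale measurement) and repeatable (<3lbs difference from day-to-day) weight measurements". A third criterion, use on more than 70% of study days, is not at issue here. The abstract (CS2.1) lists "feasibility (accuracy and repeatable measurements from the E-scale") among the primary outcomes, and section 2.17 names accuracy and repeatability as main outcome variables.

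Section 2.6 gives the sequence of weighings:
- At the first visit participants "drive onto a calibrated roll-on scale", and the chair is weighed separately and subtracted.
- Installation comes later: "Over the next few days, the study team will go to all of the subject's homes to install the E-scale under their beds".
- For the next 12 weeks "subjects will be asked to weigh themselves every day with the E-scale app".
- In week 13, "their weight will again be measured using the roll-on scale". The E-scale is removed in the days after that visit, or the participant brings it along.

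Sections T3.1 and 5.1.1 say that the device records bed weight continuously. Section 2.18 plans summary statistics for most outcomes and paired t-tests of baseline against final values. It gives no pass rule for either limit, no rule matching an E-scale reading to a laboratory weight, and no analysis separating device error from body change.

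**The concern.** The day-to-day limit is written as a property of the scale, but it is measured on people in a weight-loss programme. If the limit is missed, the data could reflect a noisy scale, ordinary variation in body weight, or both.

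The abstract says of the study: "The results could inform the refinement of this technology". Section 1.3 reports that the scale "has been tested for precision and accuracy in the laboratory", without figures, so what this study adds is performance in the home. A missed limit that cannot be assigned to scale or body does not tell the sponsor whether the scale needs refining.

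The accuracy limit has a different gap. It refers to a calibrated scale, but nothing says which E-scale reading is compared with which laboratory weight, or how far apart in time they may be.

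**Working it through.** **Inputs.** From the documents: the limits of 3 lb and 2 lb; daily readings over 12 weeks, so up to 84 readings and 83 consecutive-day pairs; at most 15 participants. The documents give no body SD, device SD or autocorrelation. I assume a within-person body SD *s* of 0.5, 1 or 1.5 lb and a lag-1 correlation *r* of 0, 0.3 or 0.5, with normal values. There is no figure in the plan to reproduce.

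**1. The two sources cannot be separated.** With independent days, body SD *b* and device SD *e*, a day-to-day difference has SD √(2(b² + e²)). The pairs (b, e) = (0, 1.5), (1.0, 1.12) and (1.5, 0) lb all give b² + e² = 2.25 after rounding, a difference SD of 2.12 lb, and P(|difference| ≥ 3) = 2(1 − Φ(3/2.12)) = 15.7%. A scale with all of the error and a scale with none give the same result.

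**2. Breach rate per pair, error-free scale.** Difference SD = s√(2(1 − r)).

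| r | s = 0.5 | s = 1 | s = 1.5 |
|---|---|---|---|
| 0 | 0.002% | 3.4% | 16% |
| 0.3 | <0.001% | 1.1% | 9.1% |
| 0.5 | <0.001% | 0.3% | 4.6% |

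**3. Effect of the unstated pass rule.** Share of participants who would fail with an error-free scale at s = 1 lb (20,000 simulated participants, 83 pairs each):

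| Rule | r = 0 | r = 0.3 | r = 0.5 |
|---|---|---|---|
| Every pair under 3 lb | 92% | 59% | 20% |
| At least 95% of pairs under 3 lb | 17% | 0.4% | <0.1% |

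At s = 0.5 lb even the every-pair rule fails at most about 0.2% of participants.

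Under a third rule, the mean absolute difference, the expected value is the difference SD × √(2/π). At r = 0 this is 0.56, 1.13 and 1.69 lb for s = 0.5, 1 and 1.5, and positive correlation lowers it. No simulated participant in this range reached 3 lb. The expected value reaches 3 lb only near s = 3/(√2 × 0.798) = 2.66 lb.

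**4. What a pass shows.** If 95% of pairs are under 3 lb, the difference SD is 3/1.96 = 1.53 lb. Its variance is at least 2e², so e ≤ 1.53/√2 = 1.08 lb. This needs device errors that are independent between days and of body weight. It does not cover slow drift. For example, an assumed 0.05 lb/day builds to 83 × 0.05 = 4.15 lb, yet at s = 1, r = 0 it moves the breach rate only from 3.39% to 3.40%.

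**5. Accuracy.** P(|difference| > 2 lb) between a laboratory weight and one error-free reading on the adjacent day:

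| r | s = 0.5 | s = 1 | s = 1.5 |
|---|---|---|---|
| 0 | 0.5% | 16% | 35% |
| 0.3 | 0.1% | 9.1% | 26% |
| 0.5 | 0.01% | 4.6% | 18% |

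Pairing with the baseline weight also adds any weight change before installation. With an assumed 3-day gap and loss of 2 lb/week, the shift is 2 × 3/7 = 0.86 lb, and the r = 0 row becomes 5.3%, 23.1% and 38.4%.

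**The case against.** The strongest reply is that Hypothesis 2b is an in-use feasibility criterion, not a bench test. The scale has already been tested in the laboratory, and a 3 lb day-to-day tolerance, wider than the 2 lb accuracy limit, can be read as allowing for ordinary variation. Body variation works against the device, so a pass is informative and only the failure branch is ambiguous. Section 2.18 speaks of summary statistics, and on a mean absolute difference the assumed body variation causes no failure. Section 2.6 also provides for troubleshooting or replacing a unit that a participant reports as malfunctioning, which gives separate evidence of gross faults. All of this stands, and it limits the weight of the point. It does not make a failure interpretable, and the documents do not say which rule applies.

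A second objection concerns the remedy. Two readings on one night share the same bedding, bed position and sensor zero, so they miss device error that differs between nights. The documents also do not say at what resolution the continuous record is kept, and section 5.1.1 says only that movement might be detectable. Both points stand. Within-night readings can supplement the day-to-day measure but cannot replace it.

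A reader might infer two stronger claims that the documents do not support:
- **That an error-free scale would probably fail.** The 92% figure needs the strictest rule, an assumed SD of 1 lb and zero autocorrelation, none of which is in the plan.
- **That no calibrated weight lies close to an E-scale reading.** Daily weighing runs up to the week-13 visit, so a reading from shortly before it should usually exist, even if the unit is brought to the laboratory. What is missing is the pairing.

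**Conclusion.** The structural point holds without any outside figure: the day-to-day limit scores body change and device error together, so a clear pass bounds random device error but a failure does not identify its cause. The practical size cannot be determined from the documents. At an assumed SD of 1 lb, the share of participants failing with an error-free scale runs from 92% to nil, depending on pass rule and autocorrelation. At 0.5 lb it is negligible under every rule considered.

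The accuracy limit has a usable reference in the week-13 roll-on weight, and lacks only a stated pairing. Drift that has built up to several pounds by week 13 would show in that pairing rather than in the day-to-day measure.

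The point is worth fixing because accuracy and repeatability are a stated primary outcome and the data needed are largely collected already. Its impact is limited: section 3.12 describes the study as exploratory, enrolment is at most 15, and the efficacy weights do not come from the E-scale.

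**What to change.** In section 2.18:

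1. Keep the day-to-day difference as the in-use measure of device plus body variation, and state the pass rule: mean absolute difference, or a named share of pairs under 3 lb.
2. Alongside it, report repeat readings from the same night, a short fixed time apart while the person is in bed and still, as far as the continuous record is stored at that resolution. Present the result as a lower bound on device error, taking body change over the interval as negligible, and state that it does not capture device error between nights. Two readings on 59 nights (70% of 84) would give one participant's within-night SD to about −15% / +22% (59 degrees of freedom, chi-square limits 0.848 and 1.220 times the estimate).
3. Pair the week-13 roll-on weight with the last E-scale reading before the visit, not the pre-installation baseline weight. Report the percentage within ±2 lb with Bland-Altman limits of agreement. State that up to a day of body variation remains in each pair.

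With 15 pairs each limit of agreement has standard error SD × √(1/15 + 1.96²/28) = 0.452 SD. Multiplied by t(14) = 2.145, this is about ±0.97 SD of the differences, so the limits will be wide.

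A known load placed on the bed at a home visit already planned would be an optional extra check of the unit; it is not part of the required change.

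The cost is a few sentences and a little more analysis. No visit is added, and participants can still bring the unit to the laboratory.

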[\[reviewer notes→\]](#)

2.12 **Does this research study involve any type of planned deception?**

If Yes, you are required to request an alteration of the informed consent process (question 4.7)

* No

[\[reviewer notes→\]](#)

2.13 **Does this research study involve the use of UPMC/Pitt protected health information that will be de-identified by an IRB approved "honest broker" system?**

* No

[\[reviewer notes→\]](#)

2.14

Will protected health information from a UPMC/Pitt HIPAA covered entity be accessed for research purposes or will research data be placed in the UPMC/Pitt medical record?

* No

2.14.1

Will protected health information from a non-UPMC/Pitt HIPAA covered entity be obtained for research purposes or will research data be placed in the non-UPMC/Pitt medical record?

* No

[\[reviewer notes→\]](#)

2.15

Does this research study involve the long-term storage (banking) of biological specimens?

* No

[\[reviewer notes→\]](#)

2.16

Will research participants be asked to provide information about their family members or acquaintances?

* No

[\[reviewer notes→\]](#)

2.17

What are the main outcome variables that will be evaluated in this study?

Subjective feedback from the survey about the usefulness and participants' satisfaction with portions of the program and E-scale.

Accuracy and repeatability of the E-scale measurements

Weight change, abdominal girth change, body-fat percentage change and Self-Rated Abilities for Health Practices (SRAHP) change

2.18

Describe the statistical approaches that will be used to analyze the study data.

* Addressed below:

Since there is only one group, most outcome variables will be analyzed using summary statistics. Baseline and final measurements will also be analyzed using paired t-tests.

[\[reviewer notes→\]](#)

2.19

Will this research be conducted in (a) a foreign country and/or (b) at a site (e.g., Navajo Nation) where the cultural background of the subject population differs

substantially from that of Pittsburgh and its surrounding communities?

- * No

Note that copies of training records, licenses, certificates should be maintained in the study regulatory binder and are subject to audit by the Research Conduct and Compliance Office (RCCO).

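### Does the ±2 lb accuracy criterion fail because no E-scale reading is tied to a calibrated weighing?

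*Combined protocol and SAP*

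**What the plan says.** Section 1.2, Hypothesis 2b, defines feasibility partly by weights that are "accurate (+/- 2 lbs. from a calibrated scale measurement". It adds a day-to-day repeatability limit of under 3 lb and use on more than 70% of study days. Section 2.17 lists "Accuracy and repeatability of the E-scale measurements" among the main outcome variables. Section 2.18 plans summary statistics for most outcomes in this single group of up to 15 people.

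Section 2.6 gives the timeline:

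- **Baseline lab visit.** Weight is obtained by "having the subjects drive onto a calibrated roll-on scale to get the weight of their chair with them in it", and the weight of the empty chair is then subtracted.
- **The following days.** After that visit, "the study team will go to all of the subject's homes to install the E-scale under their beds".
- **The next 12 weeks.** During this period "subjects will be asked to weigh themselves every day with the E-scale app".
- **Week 13, in the lab.** At this visit "their weight will again be measured using the roll-on scale".
- **Device removal.** "Over the next few days, the study team will visit all of the subject's homes to remove the E-scales"; alternatively, participants may bring the units to the lab.

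Sections T3.1 and 5.1.1 add that the device records bed load continuously, not only when the participant opens the app.

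**The concern.** An agreement limit of ±2 lb has a definite meaning only once the two measurements are named, and sections 1.2, 2.6 and 2.18 do not name them. There are two calibrated weighings and many home readings.

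The baseline weighing cannot give a contemporaneous pair, because the device is not yet under the bed. At week 13 a pair is possible but not required, and no maximum gap is set. The removal wording ("remove the E-scales or the participants can bring them with them to the lab") also allows a participant to arrive with the unit already off the bed.

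Two things would be at stake. In a study meant to reduce weight, a lagged pair mixes true change with device error. And with no stated rule, the pairing could in principle be chosen after the data are seen.

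**Working it through.** The plan gives no figure for this criterion to reproduce: section 3.12 says no sample size calculation was done. The check has three parts.

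**1. Does the timeline supply a close pair?** The baseline visit, with the first lesson, falls in week 1. Twelve further weeks of requested daily weighing run through week 13, the week of the final lab weighing. Where staff remove the device, they do so in the days after that visit, so it is still under the bed on the visit day. Where the participant brings it in, it can have been in use the night before. A same-day or night-before reading is therefore the normal result.

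**2. How often would one be missing?** Let p be the chance of a reading on any given day, with days assumed independent. The chance of at least one reading in a k-day window is 1 − (1 − p)^k. The 70% value is the use threshold in Hypothesis 2b; 50% and 90% are assumed to show the range.

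| p | 1 day | 2 days | 3 days |
|---|---|---|---|
| 0.50 | 50% | 75% | 87.5% |
| 0.70 | 70% | 91% | 97.3% |
| 0.90 | 90% | 99% | 99.9% |

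At p = 0.70, a 2-day window gives 15 × 0.91 = 13.7 of 15 participants, and a 3-day window gives 15 × 0.973 = 14.6. If readings were missed independently, all 15 would have a pair with probability 0.91^15 = 0.24 (2 days) or 0.973^15 = 0.66 (3 days). Continuous bed-load recording could raise these figures, because it does not depend on the app being opened.

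**3. What does a short gap cost?** Assume a perfect device, a per-occasion body-weight SD of s, independent fluctuation at the two weighings, and loss at 1 or 2 lb per week. The difference is then normal with mean m = gap in days × rate / 7 and SD s√2. The share within the limit is P(|difference| ≤ 2).

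The documents give no SD. A rough ceiling comes from the repeatability limit: if 95% of day-to-day differences were under 3 lb (the 95% is an assumption), s would be at most 3 / (1.96 × √2) = 1.08 lb.

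| s (lb) | No gap | 1 day (1 / 2 lb per week) | 3 days (1 / 2 lb per week) |
|---|---|---|---|
| 0.5 | 99.5% | 99.4% / 99.2% | 98.7% / 94.7% |
| 1.0 | 84.3% | 84.1% / 83.4% | 82.4% / 76.9% |
| 1.08 | 81.0% | 80.8% / 80.2% | 79.2% / 74.2% |

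The largest 1-day loss is 0.8427 − 0.8343 = 0.8 points. Three-day losses run from 0.9 to 7.4 points. At s = 1 the expected count within ±2 lb among 15 is 12.6 with no gap and 12.4 or 11.5 with a 3-day gap, so 0.3 to 1.1 fewer.

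**How to read the table.** Only the differences across a row bear on the question; the levels should not be used as a benchmark for setting a pass proportion. The 3 lb limit concerns E-scale against E-scale, so its spread includes device noise as well as body weight. If half that variance were device noise, the no-gap share for a perfect scale at the 1.08 lb anchor would be P(|N(0, 1.08)| ≤ 2) = 94%, not 81%. Weights taken close together also share fluctuation: with correlation 0.5 at s = 1, the SD of the difference is √(2 × 0.5) = 1 and the no-gap share is 95.4%, not 84.3%.

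**The case for a change.** The strongest contrary case is that a main outcome with a numeric limit should have its operational definition in writing, and that here it would cost one sentence and one requested reading. The study counts use on just over 70% of days as success. At exactly 70%, with independent days, a same-day app reading would exist for only 10.5 of 15 participants on average. A participant who takes the unit down early, or skips the last days, leaves the analyst with a longer gap. Earlier laboratory testing, mentioned in section 1.3, does not settle accuracy in homes.

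Part of this stands. The visible text has no pairing rule, and a contemporaneous pair is likely rather than assured. People without a week-13 lab weight contribute no close pair at all, which a pairing rule would not cure.

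The rest carries less weight. The 70% figure counts same-day readings only; allowing a 2-day window raises it to 91%, at a cost of under 1 point. The early-removal case is possible, but nothing in the documents suggests it would be common. Using the baseline weight as the reference would be an evident mistake, since the device was not then installed. Exact intervals, mean bias and limits of agreement would elaborate the planned summary statistics, but on at most 15 pairs they would be imprecise: even 15 of 15 within the limit gives an exact 95% interval of 78% to 100%. The study flow chart is an upload that is not shown, so a rule may already be stated there.

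**Conclusion.** The observation about the text is correct, but it does not call for a change. The plan's own schedule normally yields a same-day or night-before reading beside the week-13 lab weight, and comparing those two is the natural analysis. Filling the gap that way costs under 1 percentage point of expected agreement. A 3-day gap costs about 1 to 7 points, or roughly one participant in 15 at most at an SD of 1 lb. Section 3.12 describes the study as exploratory, no pass proportion is attached to the criterion, and no decision rule turns on a difference of that size.

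This rests on assumed loss rates of 1 to 2 lb per week, assumed per-occasion SDs of 0.5 to 1.08 lb, independent fluctuation between weighings, and daily use near or above the plan's 70% threshold. If many participants stopped using the device well before the final visit, fewer close pairs would exist. That would already show as a failure of the use criterion.
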